In REVISE, patient-important upper gastrointestinal bleeding occurred more frequently than clinically-important upper gastrointestinal bleeding. While studies have reported risk factors for clinically-important upper gastrointestinal bleeding [14], the risk factors for patient-important upper gastrointestinal bleeding, as defined by ICU survivors and family members, remain unknown. While some bleeding events confer an increased risk of death [15], most bleeding ICU patients do not die with or from gastrointestinal bleeding [11]. Dying is nonetheless a competing risk for bleeding, and dying is more common than bleeding. Thus, the primary objective of the current study is to identify risk factors for patient-important upper gastrointestinal bleeding among invasively ventilated critically ill adults, taking into account illness severity and the competing risk of death.

Materials and Methods

Risk Factor Analysis

This pre-planned secondary analysis of the REVISE trial data will be guided by this protocol. The inception cohort will comprise the 4,821 participants in the REVISE trial. These were critically ill patients who were receiving invasive mechanical ventilation patients in the ICU, who were expected to remain ventilated beyond the calendar day after randomization, and were without a clear indication or contraindication to pantoprazole [12,13].

We will use Cox proportional hazards regression analysis to assess the effect of candidate risk factors on the hazard rate of the primary outcome of time to patient-important upper gastrointestinal bleeding, considering the competing risk of death [16,17]. In REVISE, approximately 10 times as many patients died at 90-days than experienced upper gastrointestinal bleeding. The main analysis will then be a competing risk analysis for the competing risk of death [18]. The proportional hazards assumption (which states that the effects of the time-dependent variables remain stable over time) will be assessed and handled appropriately using time-varying effects [19]; alternative methods will be used if this is not satisfactory [20]. We will also assess collinearity of the independent variables (e.g., therapeutic anticoagulation and coagulopathy).

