A secondary analysis will be to determine risk factors for the secondary outcome of clinically-important upper gastrointestinal bleeding. We defined clinically-important upper gastrointestinal bleeding as the presence of overt bleeding (hematemesis, overt nasogastric bleeding, melena, or hematochezia) and at least one of the following within 24 hours in the absence of another cause: spontaneous decrease in invasively monitored mean arterial pressure or non-invasive systolic or diastolic blood pressure of 20 mmHg or more or an orthostatic increase in pulse rate of 20 beats/minute and a decrease in systolic blood pressure of 10 mmHg, with or without vasopressor initiation or increase; vasopressor initiation; a decrease in hemoglobin of ≥ 20 g/L in a 24-hour period or less; transfusion of ≥ 2 units of packed red blood cells within 24 hours of bleeding, or therapeutic intervention (e.g., angio-embolization, surgery or endoscopic treatment of bleeding) [12]. Each bleed was reviewed in duplicate by an adjudication committee, blinded to study drug, to determine whether the clinically-important upper gastrointestinal bleeding criteria were fulfilled [22].

Among 4,821 patients, 109 (2.2%) had an event which were adjudicated as clinically-important upper gastrointestinal bleeding, 5 of whom bled on the ward prompting ICU readmission. These 5 patients will be censored at ICU discharge, as daily data for the time-dependent risk factors were not collected beyond the index ICU admission.

Independent Variables:

Bleeding risk factors will include both baseline and time-dependent variables. Factors will draw on pathophysiologic rationale and prior literature. Given the number of patient-important upper gastrointestinal bleeds, we have taken into account the suitable number of independent variables to avoid an over-fitted model [23]. The same risk factors will be analyzed for the secondary outcome of clinically-important upper gastrointestinal bleeding as for the primary outcome of patient-important upper gastrointestinal bleeding.

Baseline Variables

- 1) APACHE II score (considered as a continuous variable)
- 2) Medical vs. surgical/trauma (considered as 2 categories)
- 3) Pantoprazole versus placebo as randomized (considered as 2 categories)

Time-dependent Variables

- 1) Respiratory failure, defined as receiving invasive mechanical ventilation (considered as 2 categories)

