- 2) Circulatory failure, defined as receiving inotropes or vasopressors (any dose of any of norepinephrine, epinephrine, phenylephrine, vasopressin, dopamine, dobutamine or milrinone) (considered as 2 categories)
- 3) Renal failure including acute kidney injury or end-stage renal disease, defined as receiving renal replacement therapy (any of intermittent hemodialysis [IHD], continuous renal replacement therapy [CRRT], sustained low efficiency dialysis [SLED] or peritoneal dialysis) (considered as 2 categories)
- 4) Enteral nutrition in mL/day (considered as a continuous variable)

- 5) Therapeutic anticoagulation, defined as therapeutic unfractionated heparin or low molecular weight heparin, fondaparinux, warfarin, non-vitamin K antagonist oral anticoagulants including anti-Xa inhibitors and direct thrombin inhibitors, and thrombolytic therapy (considered as 2 categories)
- 6) Coagulopathy, defined as international normalized ratio (INR) > 3.0 or prothrombin time (PTT) > 70 seconds (considered as 2 categories)
- 7) Severe thrombocytopenia, defined as platelet count $< 50 \times 10^9/L$ (considered as 2 categories)
- 8) Platelet aggregation inhibitors, defined as receipt of any of acetyl salicylic acid, clopidogrel, dipyridamole, ticlopidine, tirofiban, P2Y12 inhibitors, or non-steroidal anti-inflammatory drugs (considered as 2 categories)
- 9) Corticosteroids, defined as any corticosteroid drug or dose, either enteral or intravenous administration (considered as 2 categories)

Sensitivity Analyses

- 1) To evaluate the effect of the competing risk of death, we will conduct an analysis that does not consider the competing risk of death.
- 2) To evaluate the influence of risk factors more proximate to the bleed, we will evaluate all time-dependent risk factors defined as any time in the preceding 2 days, instead of the preceding 3 days.

Secondary Analyses

- 1) To evaluate risk factors for clinically-important upper gastrointestinal bleeding, we will repeat the same analysis [11].
- 2) To evaluate whether enteral nutrition attenuates the effect of pantoprazole on bleeding prevention compared to placebo, we will include an interaction term between pantoprazole vs. placebo and amount of enteral nutrition received [24,25].

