In this study, we will examine baseline and time-dependent risk factors for patient-important upper gastrointestinal bleeding, including the effect of pantoprazole versus placebo. Use of the REVISE trial database will build on risk factor analyses of clinically-important upper gastrointestinal bleeding from prior large trials [25,29].

Strengths of this study include the focus on an outcome developed by ICU survivors and relatives of ICU survivors or decedents. We will minimize the risk of over-fitted regression models caused by evaluation of many admitting diagnoses. Beyond assessing baseline characteristics, we will use Cox models to assess interventions and key laboratory values reflecting events and exposures over the ICU stay. Although proton-pump inhibitors for bleeding prophylaxis do not affect 90-day mortality overall as shown in a recent meta-analysis (RR 0.99 [95% CI, 0.93 to 1.05]) [30], within-trial subgroup analysis suggests a possible heterogeneity of treatment effect based on disease severity. Accordingly, the main analysis will address the competing risk of death and a sensitivity analysis will evaluate whether this impacts the results. In this contemporary database, half of the patients were randomized to no stress ulcer prophylaxis, enabling the evaluation of risk factors with and without stress ulcer prophylaxis. This study will address some issues proposed for future research on this topic [31], including evaluating the volume of enteral nutrition (e.g., trophic versus full feeding) and special populations (e.g., acute hepatic failure). Heterogeneous patients from 68 international centers will increase the generalizability of the results.

Limitations of this study include no information on some uncommon exposures in the REVISE trial (e.g., non-invasive ventilation) and on some rare conditions (e.g., admitting diagnosis of organ transplantation). To focus on events that consume healthcare resources, we will not address overt bleeding, which often resolves; if it evolves into patient-important or clinically-important upper gastrointestinal bleeding, these events will be included in this analysis. This study is not designed to construct or both construct and validate a prediction model, which requires a different design. All analyses such as these are subject to confounding, yielding information on association rather than causation, needing cautious interpretation.

Conclusions

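### The pantoprazole-by-feeding interaction could pick up variation in pantoprazole's effect by circulatory failure, and the plan has no check for this

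*Combined protocol and SAP*

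**What the plan says.** Secondary Analyses, item 2, gives the aim as "To evaluate whether enteral nutrition attenuates the effect of pantoprazole on bleeding prevention compared to placebo" and the method as "we will include an interaction term between pantoprazole vs. placebo and amount of enteral nutrition received". No other product term with pantoprazole is named there.

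The component variables are defined under Independent Variables:
- Baseline Variables, item 3: "Pantoprazole versus placebo as randomized (considered as 2 categories").
- Time-dependent Variables, item 4: "Enteral nutrition in mL/day (considered as a continuous variable").
- Time-dependent Variables, item 2: "Circulatory failure, defined as receiving inotropes or vasopressors", two categories, entered as a main effect.

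APACHE II is also a main effect only. For effects that change over time, Risk Factor Analysis says that the proportional-hazards assumption "will be assessed and handled appropriately using time-varying effects", with other methods if that fails. The parenthesis glosses the assumption as one "which states that the effects of the time-dependent variables remain stable over time".

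The Results section calls the analyses exploratory and promises cautious reading. The Discussion says that they can show association but not cause.

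**The concern.** Treatment is randomised, but EN volume is a post-randomisation exposure that nobody assigned. A main-effect term for circulatory failure adjusts the EN main effect. It does not adjust the pantoprazole x EN product; that would need pantoprazole x circulatory failure in the model. Without it, a pantoprazole effect that differs between patients with and without circulatory failure can be carried by whatever correlates with circulatory failure, and EN volume is a candidate.

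At stake is the reading of the plan's pre-specified effect-modification question: whether fed patients still gain from prophylaxis. The error can go either way. If pantoprazole works better in circulatory failure and such patients receive less EN, feeding appears to attenuate the effect. If it works less well there, feeding appears to strengthen it.

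**Working it through.** The documents give no power or detectable effect for this interaction, so there is no figure of the plan's to reproduce.

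**Inputs from the documents.** Primary Outcome: 136 bleeds among 4,821 patients (136/4,821 = 2.8%, as stated), 5 censored at ICU discharge, leaving 131. Introduction: pantoprazole HR 0.36. Results: two-sided alpha 0.05. Model size: 3 baseline + 9 time-dependent + 1 product = 13 parameters.

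**Inputs assumed, because the documents give none.** Circulatory failure on 40% of days with bleeding HR 2.5; EN standard deviation 450 mL/day; EN HR 0.8 per 500 mL/day; a range of EN-shock correlations; a range of ratios of pantoprazole's HR with versus without circulatory failure. The true EN interaction is set to 1.00 throughout.

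**Mechanism.** Let A be pantoprazole, S circulatory failure and X EN per 500 mL/day. Suppose the log hazard contains g·A·S but no A·X term. With A·S left out and 1:1 allocation, the fitted A·X coefficient is, to first order, g x (slope of S on X), where the slope is corr(S,X) x SD(S)/SD(X). It is zero if g = 0 or the correlation is 0.

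Hand check at correlation -0.44 and HR ratio 2: SD(S) = sqrt(0.4 x 0.6) = 0.490; SD(X) = 450/500 = 0.9; slope = -0.44 x 0.490/0.9 = -0.240; ln 2 x -0.240 = -0.166; exp(-0.166) = 0.85. A large-sample Poisson fit (equivalent to Cox), scaled to 131 events, gives 0.859 with SE 0.245. Then z = |ln 0.859|/0.245 = 0.62, and rejection = Φ(-1.96 + 0.62) + Φ(-1.96 - 0.62) = 0.090 + 0.005 = about 9.5% (9.6% from the fit).

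**Planned model: spurious EN ratio per 500 mL/day, with rejection rate**

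| EN-shock correlation | HR ratio 1 | 1.5 | 2 | 3 |
|---|---|---|---|---|
| 0 | 1.00, 5.0% | 1.00, 5.0% | 1.00, 5.0% | 1.00, 5.0% |
| -0.19 | 1.00, 5.0% | 0.96, 5.3% | 0.93, 5.9% | 0.91, 6.8% |
| -0.44 | 1.00, 5.0% | 0.91, 6.7% | 0.86, 9.6% | 0.80, 14.7% |
| -0.61 | 1.00, 5.0% | 0.88, 8.4% | 0.82, 13.9% | 0.74, 24.2% |

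Opposite direction (pantoprazole works better in circulatory failure): HR ratio 0.5 at -0.44 gives 1.19, 11.7%; HR ratio 0.33 at -0.61 gives 1.43, 40.4%. With pantoprazole x circulatory failure added, every cell returns to 1.00 and 5%.

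A separate patient-level simulation (400 replicates, lagged 3-day mean EN) agrees. HR 0.25 in shock versus 0.70 otherwise gave a false ratio of 1.62 per 1,000 mL/day, 32% significant. HR 0.50 versus 0.20 gave 0.67, 16%. A milder split, 0.30 versus 0.45 in either direction, gave 8.5-9.5% in a further simulation.

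**Time path.** Take HR ratios (days 1-4 versus later) of 1.5 to 3, with EN rising over the first days. If no proportional-hazards step ran, rejection would be 7.5% to 24.0% at an early-period/EN correlation of -0.44, and 9.7% to 39.3% at -0.61. The power of a pantoprazole x time check with 131 events is about 17%, 41% and 75-77% at ratios 1.5, 2 and 3. The check and the false interaction arise from the same data, however. In a simulation of 200 replicates with strong time patterns, adding pantoprazole x log(day) whenever the check was significant cut false positives from 37% to 8.5% (HR 0.20 then 0.60) and from 40% to 11.5% (HR 0.60 then 0.25).

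**Cost of the extra terms.** Events per parameter: 131/13 = 10.1; 131/14 = 9.4; 131/15 = 8.7. SE of the EN term per 500 mL/day with pantoprazole x circulatory failure added: 0.240 to 0.265 at -0.44 (1.1 times), 0.226 to 0.284 at -0.61 (1.26 times). In the 400-replicate simulation with both extra terms: 0.36 to 0.53 per 1,000 mL/day (1.5 times).

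**The case against.** The strongest reply is that the plan does not overclaim. A reader might infer that the analysis will report feeding as the cause of any attenuation. The documents do not support that: the Results section calls the work exploratory and the Discussion limits it to association. This stands. But a general caveat does not tell a reader whether an observed interaction tracks feeding, circulatory failure or study day.

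A reader might also infer that time is ignored. It is not. The proportional-hazards step could bring in pantoprazole x time, and it removes most of the excess if it is applied to pantoprazole. What remains open is its scope: it is conditional, its parenthesis speaks of time-dependent variables while pantoprazole is listed as a baseline variable, and it is not said to be repeated for the interaction model.

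A reader might take the Discussion's remark that "within-trial subgroup analysis suggests a possible heterogeneity of treatment effect based on disease severity" as evidence of heterogeneity here. That sentence concerns mortality, and the plan answers it with competing-risk handling. It does not show that pantoprazole's effect on bleeding varies by circulatory failure.

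Finally, the larger rates depend on strong assumed inputs, and the Independent Variables section deliberately limits the number of terms. Both points stand. They argue for a sensitivity fit rather than a change to the planned model.

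**Conclusion.** The gap is real but modest. The plan specifies one pantoprazole product term, and nothing in it checks whether the EN interaction reflects variation by circulatory failure. The EN interaction could be biased in either direction; the documents do not show that it would be. Bias needs both a pantoprazole effect that differs by circulatory failure and an EN-shock correlation, and the documents report neither.

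Under the assumed inputs, false positives run at about 5-10% for modest heterogeneity (1.5-fold). They reach about 15-40% only when strong heterogeneity (2.5-fold or more) meets an appreciable correlation. These figures also assume how continuous EN is summarised over the three-day window, which the plan does not define. The time path is partly protected already. This is a cheap improvement, an optional sensitivity analysis; it does not affect the primary analysis.

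**What to change.** Keep the planned model for Secondary Analyses, item 2, and add:

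1. One sensitivity fit that also includes pantoprazole x circulatory failure.
2. A statement that the proportional-hazards check in Risk Factor Analysis covers pantoprazole in the interaction model, with pantoprazole x time added where indicated.
3. The EN interaction ratios from both fits, with confidence intervals, side by side. If they differ materially, describe the EN interaction as not separable from circulatory failure or time.

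No pass/fail rule for claiming attenuation is needed. At an SE of 0.53 per 1,000 mL/day the 95% interval extends by a factor of exp(1.96 x 0.53) = 2.8 on each side, so such a rule could discard genuine attenuation through noise.

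The cost is a few sentences and one extra fit on variables already in the analysis. The loss of precision and of events per parameter shown in the working falls only on the sensitivity fit, unless the plan's own proportional-hazards step adds a time term to the planned model.

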We will include both baseline variables and time-dependent variables, described further below. All time-dependent risk factors will be defined as existing any time in the preceding 3 days, but not including the day of bleed. For bleeds that occur on day 1 of the study, we will use day 1 data to define the time-dependent covariates. We will consider ICU discharge and consent withdrawal as censoring events.

Dependent Variables:

Primary Outcome

The primary dependent variable will be patient-important upper gastrointestinal bleeding. This was defined in a mixed-methods study of ICU survivors and families [21], with gastrointestinal bleeding judged as important if bleeding resulted in a blood transfusion, vasopressor treatment, diagnostic endoscopy, CT-angiography, surgery, or if it resulted in death, disability, or prolonged hospitalization [10]. These criteria were applied to the REVISE database up to 90 days after randomization [11]. Our main analysis will include all patient-important upper gastrointestinal bleeds that occurred in the ICU.

Among 4,821 patients, 136 (2.8%) had patient-important upper gastrointestinal bleeding, 5 of whom bled on the ward prompting ICU readmission. These 5 patients will be censored at ICU discharge, as daily data for the time-dependent risk factors were not collected beyond the index ICU admission.

Secondary Outcome

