- 3) To evaluate whether certain baseline conditions are associated with patient-important upper gastrointestinal bleeding, we will include these variables in the main model one at a time: acute hepatic failure [26], traumatic brain injury [27] and female sex [28].

Missing Data

We anticipate little missing data except for 2 risk factors in patients with length of ICU stay greater than 2 weeks. Platelet aggregation inhibitors and corticosteroids were not collected from day 15 onwards 14 on the abbreviated trial case report form. For the primary analysis, if there are any patients remaining in the ICU after 2 weeks who received a platelet aggregation inhibitor on day 14, we will impute that it was continued until ICU discharge, except in the event of bleeding, assuming that the indication persisted over time (e.g., coronary artery disease). For the primary analysis, we will impute that if there are any patients receiving corticosteroid treatment on day 14, it was continued only to day 21, assuming the indication resolved (e.g., septic shock).

Results

We will report independent variables and other characteristics of participants with and without patient-important upper gastrointestinal bleeding using descriptive statistics, including means and standard deviations (or medians with interquartile ranges, if appropriate) for continuous data, and numbers with percentages for categorical data.

Figures we will present include the day of each bleed in the ICU, the concordance between patient-important gastrointestinal bleeding and clinically-important upper gastrointestinal bleeding, and the daily use of invasive ventilation and any enteral nutrition.

Regression results will be presented as adjusted hazard ratios with 95% confidence intervals and corresponding two-tailed p-values for the associations of each independent variable with the primary and secondary outcomes. The criterion for statistical significance will be set at alpha = 0.05. No corrections for multiple testing will be performed because of the exploratory nature of the analyses, but findings will be interpreted in light of confidence intervals and cautiously interpreted.

Discussion

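### Does imputing late platelet-inhibitor and corticosteroid exposure by one fixed rule per drug, with an exception for bleeding, undermine those two hazard ratios?

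*Combined protocol and SAP*

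**What the plan says.** The Missing Data section states that "Platelet aggregation inhibitors and corticosteroids were not collected from day 15 onwards" on the abbreviated case report form. It gives one rule per drug, each for the primary analysis. For a patient on a platelet inhibitor on day 14, "we will impute that it was continued until ICU discharge, except in the event of bleeding", on the ground that the indication persists. For a patient on a corticosteroid on day 14, "it was continued only to day 21, assuming the indication resolved".

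Under Risk Factor Analysis, time-dependent factors are "defined as existing any time in the preceding 3 days, but not including the day of bleed". Item 2 of Sensitivity Analyses redefines them as "defined as any time in the preceding 2 days, instead of the preceding 3 days". Item 1 drops the competing risk of death. For clinically-important bleeding, Secondary Analyses item 1 says "we will repeat the same analysis". The other two secondary analyses add a nutrition interaction and three baseline variables. None of the five alters an imputation rule.

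The Primary Outcome section reports that "136 (2.8%) had patient-important upper gastrointestinal bleeding, 5 of whom bled on the ward prompting ICU readmission"; those 5 are censored at ICU discharge. On the model, the plan says "The main analysis will then be a competing risk analysis for the competing risk of death".

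**The concern.** Two features look troublesome.

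First, for 2 of the 12 covariates (3 baseline, 9 time-dependent), every value used late in the ICU stay is an assumption, and no planned run shows how the hazard ratios respond to it. The 2-day window does not test the rules; it relies on them one day sooner.

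Second, the platelet-inhibitor rule mentions bleeding, which is the outcome. A time-dependent covariate in a Cox model must be fixed by what has happened before the day in question. If patients who later bleed were denied the carry-forward while comparable non-bleeders kept it, late bleeders would be coded unexposed and late non-bleeders exposed. That would pull the platelet-inhibitor hazard ratio toward apparent protection. Because the authors hope the results may inform bedside care and guidelines, a spurious protective association would matter.

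**Working it through.** **Plan's own figures.** 136/4,821 = 2.8%, as stated. ICU bleeds in the main analysis: 136 − 5 = 131, or 131/12 = 10.9 per covariate.

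**When imputation takes over.** For index day t the window is t−3 to t−1. Uncollected days (15 or later) number 0 of 3 on day 15, 1 on day 16, 2 on day 17 and 3 from day 18. With the 2-day window, exposure is wholly imputed from day 17. A day-14 corticosteroid user is coded exposed through index day 24 and unexposed from day 25 (window days 22 to 24).

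**What the exception does.** Take a counted bleed on day 20. Its window is days 17 to 19. If continuation ends at discharge or at the bleed, day-14 status is carried through day 19 for this patient, exactly as for everyone else at risk on day 20. Day 20 itself is not used. The exception therefore has no effect on this comparison.

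**Size of ordinary misclassification.** The documents give neither prevalence nor bleed timing, so these are assumptions:
- coded prevalence p = 0.30 throughout;
- true hazard ratio 1.5;
- share f of bleeds on day 18 or later: 5% to 30%;
- among those coded exposed late, a share s = 0.3 or 0.5 has stopped;
- among those coded unexposed, t = 0.1 has started;
- a cause-specific risk set and a single binary covariate.

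Formulas:
- late hazard ratio = [(1−s)·1.5 + s] / [t·1.5 + 1 − t], giving 1.35/1.05 = 1.29 or 1.25/1.05 = 1.19;
- exposed share among bleeds, q = p·HR / (p·HR + 1 − p);
- pooled share Q = (1−f)·q(early) + f·q(late);
- pooled HR = Q(1−p) / [(1−Q)p].

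Example, f = 0.30 and s = 0.5: q(early) = 0.45/1.15 = 0.3913; q(late) = 0.3571/1.0571 = 0.3378; Q = 0.7 × 0.3913 + 0.3 × 0.3378 = 0.3753; HR = (0.3753 × 0.7)/(0.6247 × 0.3) = 1.40.

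To represent bleeders left out of the carry-forward, set q(late) = 0. At f = 0.30, Q = 0.2739 and HR = (0.2739 × 0.7)/(0.7261 × 0.3) = 0.88.

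| Late share | Late bleeds of 131 | HR, continued to discharge (s = 0.3 to 0.5) | Ratio to 1.50 | HR if bleeders left out |
|---|---|---|---|---|
| 5% | 7 | 1.49–1.48 | 0.99 | 1.38 |
| 10% | 13 | 1.48–1.47 | 0.98 | 1.27 |
| 20% | 26 | 1.46–1.43 | 0.97–0.96 | 1.06 |
| 30% | 39 | 1.43–1.40 | 0.96–0.93 | 0.88 |

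Coding the same patients as stopped after day 14 leaves nobody exposed from day 18, so late bleeds add nothing and the estimate stays at 1.50. The fourth column is therefore also the gap between the two rules. For the day-21 rule, with half the late bleeds on day 25 or later, the estimates are 1.49 / 1.49–1.48 / 1.48–1.46 / 1.46–1.44.

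**Against sampling error.** SE(log HR) = 1/√(131 × 0.3 × 0.7) = 0.191, so the 95% limits lie a factor exp(1.96 × 0.191) = 1.45 either side. The largest shift, ln(1.50/1.40) = 0.069, is about 0.36 of one standard error.

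**What an all-stopped run would offer.** At a 30% late share, these two hazard ratios would draw on about 92 bleeds, and the factor widens to exp(1.96/√(92 × 0.21)) = 1.56. A difference from the main model could also reflect effects that change over time.

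**The case for a change.** The best case for a change is this. The plan itself singles out these two covariates as its exception to little missing data, then offers no analysis that probes them. The persistence argument rests on coronary disease, yet the covariate also includes non-steroidal anti-inflammatory drugs. The kind of bleeding meant is not defined, and the value for patients not on the drug on day 14 is only implied. One possible reading of the exception can erase or reverse a hazard ratio. Rewording costs nothing, and two more model runs need no new data.

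The factual parts stand; they are missing detail. The damaging reading does not: the exception qualifies how long treatment is taken to continue, and nothing says that future bleeders are excluded. Its one working function would be to end imputed exposure at an earlier bleed that is not the counted event, such as an overt bleed, or a patient-important bleed in the analysis of clinically-important bleeding. That uses only past information and is legitimate. A blanket rule carrying exposure through every bleed before the counted one would remove this function, and if applied to both drugs it would clash with the corticosteroid stop at day 21.

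The extra runs would look for a shift well inside sampling error, and neither an all-stopped nor an all-continued run covers patients who start a drug after day 14.

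**Conclusion.** No change is needed. The observations are right: both covariates are wholly imputed from day 18 (day 17 with the shorter window), and one rule per drug runs through every listed analysis. Followed as naturally read, the plan still gives usable estimates. Under the stated assumptions, the choice between continuing and stopping moves each hazard ratio by a ratio of 0.99 to 0.93, against a 95% confidence factor of 1.45. The interval in the full 12-covariate model is probably wider still. The fall to 1.38–0.88 would be the result of misprogramming; it is not a property of the plan. Which bleed ends exposure, and that day-14 non-recipients are coded unexposed, are details an analyst settles sensibly in the programming specification.

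The plan also discloses the gap, gives a reason for each rule, will plot the day of each bleed, calls the analyses exploratory and limits its claims to association.

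The conclusion rests on assumed prevalence, late share, stopping and starting rates. The figures are for a cause-specific risk set. The plan specifies a competing-risk main analysis and cites the subdistribution model; the sizes were not worked out for that risk set.
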